### **3.1.2 Treatment Phase**

The treatment phase begins with the randomization call to the IVRS. The subject is randomly assigned to one of the two treatment arms. Study treatment must begin within 3 days of randomization.

Nivolumab 240 mg IV is administered as a 30-minute IV infusion every 2 weeks. Sorafenib 400 mg is administered twice a day. Both study drugs are continued until disease progression, unacceptable toxicity, withdrawal of consent or study closure. Study assessments are to be collected as outlined in [Table 5.1-2](#) and [Table 5.1-3](#).

Nivolumab or sorafenib treatment beyond initial investigator-assessed RECIST 1.1-defined progression is permitted if the subject has investigator assessed clinical benefit and is tolerating study drug, as specified in [Section 3.1.6](#). Specific requirements for subjects treated with nivolumab and sorafenib, including dose modifications, dose delays, and treatment discontinuation criteria are described in [Sections 4.5.1](#) and [4.5.3](#), respectively.

The treatment phase ends when the subject is discontinued from study drug (see [Section 3.5](#)). Subjects will then enter the Study Follow-Up Phase.

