### **3.1.3 Follow Up Phase**

This phase begins when the decision to discontinue study drug is made. Two follow up visits are required, occurring 35 days  $\pm$  7 days from the last dose (X01) and 80 days  $\pm$  7 days from X01 (X02). Follow up visits include targeted physical examination, laboratory tests, tumor assessments, adverse event and concomitant medication assessments, and PRO instrument collection. Additional details and requirements are outlined in [Table 5.1-4](#). After completion of the first two follow-up visits, subjects will be followed every 3 months for survival, as outlined in [Table 5.1-4](#).

Subjects who discontinue study drug for reasons other than radiographic disease progression will continue to have tumor assessments (if clinically feasible) according to the schedule in [Table 5.1-2](#) and [Table 5.1-3](#) until progression.

Subjects will be followed for drug-related toxicities until these toxicities resolve, return to baseline or are deemed irreversible. All adverse events will be documented for a minimum of 100 days after the last dose of study drug.

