Procedure	During Treatment (Cycle = 2 weeks)  Cycle 1 - Day 1 (C1, D1), Cycle 2 - Day 1 (C2 D1), (and every cycle thereafter)	Notes
Peripheral blood mononuclear cells (PBMCs) and myeloid derived suppressor cells (MDSCs)	Cycle 1, Day 1	See sections 5.6.2.3 and 5.6.2.4 , and Table 5.6.2-1 for details
Outcomes Research Assessment		Questionnaires should be administered at the start of the visit, before the subject sees the physician and before any study related procedures are done (with the exception of procedures completed 72 hours prior to visit).
EQ-5D-3L	See Note	To be completed on Cycle 1, Day 1, then every other cycle thereafter (Cycle 3, Day 1; Cycle 5, Day 1, etc.)
FACT-Hep	See Note	To be completed on Cycle 1, Day 1, then every other cycle thereafter (Cycle 3, Day 1; Cycle 5, Day 1, etc.)
Health care resource use (HCRU)	X	
Clinical Drug Supplies		
Contact central randomization IVRS / Dispense Study Drug	X	Within 3 days from randomization, the subject must receive the first dose of study medication.  Subjects may be dosed no less than 12 days between doses.

Table 5.1-3: On treatment Period Procedural Outline - Sorafenib (CA209459)		
Procedure	During Treatment: (Cycle = 2 weeks)  Cycle 1 - Day 1 (C1, D1), Cycle 2 - Day 1 (C2 D1), (and every cycle thereafter)	Notes
Safety Assessments		
Targeted Physical examination	X	Targeted examination must include at a minimum the following body systems: Cardiovascular Gastrointestinal Pulmonary Skin
Physical Measurements	X	Weight and ECOG performance status
Child-Pugh Score	X	
Vital Signs	X	Including BP, HR, temperature, and respiratory rate. BP monitoring frequency should follow local standards of care as guided by the locally approved sorafenib product label or applicable SmPC. 
2D Echocardiogram	See note	2-D echocardiogram, performed locally as clinically indicated.
Adverse Events Assessment	X	
Review of Concomitant Medication	X	

Table 5.1-3: On treatment Period Procedural Outline - Sorafenib (CA209459)		
Procedure	During Treatment: (Cycle = 2 weeks)  Cycle 1 - Day 1 (C1, D1), Cycle 2 - Day 1 (C2 D1), (and every cycle thereafter)	Notes

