Tumor imaging assessment	See Note	See Note	
Tumor imaging assessments during Follow Up and Survival Follow up is required for subjects that have discontinued treatment prior due to reason other than radiologic disease progression.
 
Tumor imaging assessments will occur 8 weeks from the date of randomization (+/- 1 wk), then every 8 weeks (+/- 1 wk) thereafter up to 48 weeks, then it will be every 12 weeks (+/- 1 week) until disease progression.
 
CT of the chest, CT or MRI of abdomen, and pelvis with IV contrast, including required tri-phasic CT of the liver should be performed. CT chest without contrast or MRI abdomen/pelvis is acceptable if CT is contraindicated. Modality (CT or MRI) used at baseline should be used across all imaging timepoints. Bone scan is required if clinically indicated.
 
Subjects with a history of brain metastasis may have surveillance MRI approximately every 12 weeks from the date of first dose, or sooner if clinically indicated

Other Assessments			
PK/IMG sampling	X		To be collected for nivolumab subjects only. See Section 5.5.1

Table 5.1-4: Follow-Up Procedural Outline - all subjects (CA209459)			
Procedure	Follow Up, Visits 1 and 2 (X visits)a	Survival Follow Up Visits (Y visits)b	Notes
Outcomes Research Assessment			The EQ-5D and FACT-Hep should be administered at the start of the visit, before the subject sees the physician and before any study related procedures are done
EQ-5D-3L	X	X	EQ-5D to be assessed during clinical visit or via a phone for survival follow-up visits
FACT-Hep	X	X	FACT-Hep to be assessed during clinical visit or via a phone for survival follow-up visits
Health care resource use (HCRU)	X		Health Care Resource Use (HCRU) to be assessed during clinical visit
Subject Status			
Survival Status		X	Every 3 months after FU 2; may be accomplished by visit or phone contact

a X visits occur as follows: X01 = 35 days ± 7 days from last dose, X02 = 80 days ± 7 days from X01

b S, Survival visits continue every 3 months after X visits

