#### **8.4.6 Outcomes Research Analyses**

The analysis of EQ-5D and FACT-Hep data will be performed in all randomized subjects who have an assessment at baseline (Day 1, assessment prior to administration of drug on day of first dose) and at least 1 subsequent assessment while on treatment. Questionnaire completion rate, defined as the proportion of questionnaires actually received out of the expected number, will be calculated and summarized at each assessment point.

EQ-5D data will be described by treatment group as randomized in the following ways:

- EQ-5D index scores will be summarized at each assessment time point using descriptive statistics (ie, N, mean with standard deviation and 95% CI, median, first and third quartiles, minimum, maximum).
- EQ-VAS scores will be summarized at each assessment time point using descriptive statistics (ie, N, mean with standard deviation and 95% CI, median, first and third quartiles, minimum, maximum).
- The proportion (N) of subjects reporting no, moderate, or extreme problems will be presented for each of the 5 EQ-5D dimensions at each assessment time point. Subjects with missing data will be excluded from the analysis.
- A by-subject listing of the level of problems in each dimension, corresponding EQ-5D health state (ie, 5-digit vector), EQ-5D index score, and EQ-VAS score will be provided.

FACT-Hep data will be described by treatment group as randomized in the following ways:

- FACT-Hep total scores will be summarized at each assessment time point using descriptive statistics (ie, N, mean with standard deviation and 95% CI, median, first and third quartiles, minimum, maximum).
- Changes from baseline in FACT-Hep total scores will be summarized at each post-baseline assessment time point using descriptive statistics (ie, N, mean with standard deviation and 95% CI, median, first and third quartiles, minimum, maximum).
- The proportion (N) of subjects achieving a change of  $\geq 8$  points (ie, MID) in FACT-Hep total score will be summarized at each post-baseline assessment time point.

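### The EQ-5D and FACT-Hep analysis set requires a later form completed on treatment, so subjects who stop study drug before Cycle 3 are left out although their follow-up forms are collected.

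*Protocol*

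**What the plan says.** Protocol 8.4.6 (Outcomes Research Analyses) defines the set for both questionnaires. A randomized subject enters with a pre-dose form on the day of first dose and "at least 1 subsequent assessment while on treatment". Results are then described by arm as randomized. The plan gives EQ-5D index and VAS summaries, the EQ-5D dimension proportions, FACT-Hep totals, changes from baseline in FACT-Hep, and the share with a FACT-Hep change of 8 points or more. All are given per assessment time point. The section also defines a completion rate as forms received over forms expected, without saying in which subjects it is computed.

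The schedule is the same in both arms. For each instrument, Tables 5.1-2 and 5.1-3 read "To be completed on Cycle 1, Day 1, then every other cycle thereafter", with Cycle 3 Day 1 named as the next visit.

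Collection continues after study drug stops. Protocol 3.1.3 states: "Follow up visits include targeted physical examination, laboratory tests, tumor assessments, adverse event and concomitant medication assessments, and PRO instrument collection". Table 5.1-4 marks both instruments at the X visits and the survival visits, with the notes "EQ-5D to be assessed during clinical visit or via a phone for survival follow-up visits" and "FACT-Hep to be assessed during clinical visit or via a phone for survival follow-up visits".

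On where treatment ends, Protocol 3.1.2 says: "The treatment phase ends when the subject is discontinued from study drug". Under Protocol 3.1.3 the follow-up phase starts with the decision to discontinue.

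**The concern.** Taken together, these sections collect data that the analysis rule then discards. A subject who stops before Cycle 3 Day 1 has no scheduled form that can meet the on-treatment condition, and so drops out of the set along with the baseline form and every follow-up form.

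The condition is met or failed after randomization and depends on remaining on drug for about four weeks. Early stopping is plausibly related to toxicity or decline, and it may differ between arms in an open-label comparison. The follow-up summaries are presented as describing the randomized arms, but they would describe the part of each arm that stayed on treatment to the first scheduled form. Protocol 5.7 says the EQ-5D data may inform economic evaluations, so the tables have a use beyond the study report.

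**Working it through.** The plan states no sample size, power or alpha for the questionnaires, so there is no figure to reproduce. The check compares the rule with the schedule and then sizes the effect under stated assumptions.

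**1. First form that can qualify.** Cycles last 2 weeks, so Cycle 3 Day 1 is day 1 + 2 × 14 = day 29 in both arms.

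**2. Where an early stopper's next forms fall.** X01 is 35 ± 7 days after last dose (Table 5.1-4).
- Last dose on day 1: X01 near day 36 (1 + 28 = 29 to 1 + 42 = 43).
- Last dose on day 15: X01 near day 50 (15 + 28 = 43 to 15 + 42 = 57).
- X02 is nominally 35 + 80 = 115 days after last dose; survival visits follow every 3 months.

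Under Protocol 3.1.2 and 3.1.3 all of these belong to follow-up, so none satisfies the rule. A subject who stops at the Cycle 3 visit itself may still qualify: the nivolumab schedule gives the forms at the start of the visit, before the physician is seen.

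**3. Which tables change.** Each summary is per time point, and the section plans no longitudinal model or imputation.
- Cycle 3, 5 and later on-treatment visits: early stoppers have no form there, so these tables are the same with or without them.
- Baseline summary: changes, because their baseline form is removed.
- X01, X02 and survival visits: scores, change from baseline and the share with a change of 8 points or more all change.
- Completion rate: changes only if it is computed in this set.

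**4. Number excluded.** With n = 363 per arm (Protocol 3.1) and an assumed proportion p stopping alive before Cycle 3 Day 1, excluded = 363 × p.
- p = 3%: 10.9, about 11.
- p = 10%: 36.3, about 36.

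The 3% to 10% range is an assumption; the documents give no rate.

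**5. Early deaths are separate.** They cannot return follow-up forms. With the design assumptions (Protocol 8.1, SAP 5), t = 28/30.4375 = 0.92 month:

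P(death by t) = 0.61 × [1 − exp(−ln2 × t/m1)] + 0.39 × [1 − exp(−ln2 × t/m2)]

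- Sorafenib, medians 10 and 14 months: 5.5%, or 20 of 363.
- Nivolumab, medians 10/0.74 = 13.5 and 14/0.74 = 18.9 months: 4.1%, or 15 of 363.

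**6. Possible shift in a mean.** If the excluded make up a share p of those who would contribute at a time point and differ from the rest by D, the mean moves by p × D. With D = 8 FACT-Hep points:
- 3%: 0.03 × 8 = 0.24
- 5%: 0.05 × 8 = 0.4
- 10%: 0.10 × 8 = 0.8

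Protocol 5.7 puts the minimally important difference for the FACT-Hep total at 8 to 9 points. The share p at a particular follow-up visit could be higher or lower than in the whole arm; the documents do not allow it to be estimated.

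**The case against.** The strongest reply is that the main tables do not move. That stands: a reader might infer that the rule makes each arm's on-treatment quality of life look better, but step 3 shows that those summaries are identical either way.

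A reader might also take the 28% permanent sorafenib discontinuation for adverse events in Protocol 1.1 as evidence of unequal early exclusion. It is an any-time figure from a real-life study, with no nivolumab counterpart beside it, and says nothing about the first four weeks.

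On-treatment is not defined for the questionnaires. SAP 7.4.3 uses a window of 100 days after last dose, and X01 at 28 to 42 days would fall inside it, which would restore subjects who return an X01 form. But that window is written for concomitant medications only, and the protocol's phase definitions put X01 in follow-up. If the wider meaning was intended, 8.4.6 needs to say so.

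The completion-rate effect is conditional. If the rate were computed in this set, baseline completion would be 100% by construction, which makes that reading doubtful, but the text does not settle it.

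Parts of the SAP are redacted, including contents entries between 7.8.1.1 and 7.10, and an outcomes-research section may be among them. No visible text brings these subjects back in. Finally, the analysis is descriptive and is not among the visible primary or secondary objectives. That limits the weight of the point but does not remove it.

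**Conclusion.** The point holds in a limited form. As written, Protocol 8.4.6 excludes subjects who stop study drug before Cycle 3 Day 1, although their forms are collected afterwards. The baseline, X01, X02 and survival-visit summaries therefore describe a set selected on staying on treatment, and so does the completion rate if it uses the same set. On-treatment summaries from Cycle 3 onward are not affected, and neither is any test or alpha.

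The size rests on an assumed early-stopping rate: 11 to 36 of 363 per arm at 3% to 10%. The direction of any difference between arms cannot be derived from the documents. The conclusion takes on-treatment in the sense of Protocol 3.1.2 and 3.1.3. This is a worthwhile low-cost improvement and does not threaten any confirmatory conclusion.

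**What to change.** In Protocol 8.4.6, replace the on-treatment condition with: *and at least one later assessment, on treatment or during follow-up (X01, X02 or a survival visit)*. Align the outcomes-research text in the SAP if there is any.

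Compute completion in all randomized subjects. Count as expected only the forms scheduled for a subject who is alive and in that phase at the time point: cycle forms while on treatment, X-visit and survival forms after discontinuation. Counting cycle forms for everyone alive would create artificial non-completion, because those forms are not scheduled off treatment.

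Report the current on-treatment set alongside. SAP 7.10 gives 05 June 2019 as the lock for the final OS analysis, so label any tables added after that date as post hoc.

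The cost is a wording change and a rerun of descriptive tables; no new data are needed. Reported completion rates may be slightly lower. The revised baseline summary would still require one later form, so some selection remains there. The follow-up-visit summaries would no longer depend on staying on treatment.

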#### **8.4.7 Other Analyses**

Methodology for exploratory analyses including immunogenicity is described in the statistical analysis plan.

### **8.5 Interim Analyses**

A formal interim analysis for the OS is planned after 416 deaths have been observed, which is expected to occur approximately 25 months after the first subject's randomization date. This formal comparison of OS will allow for early stopping for superiority. Lan-DeMets alpha spending function with O'Brien and Fleming type of boundary will be used. The stopping boundary will depend on the actual number of deaths at the time of the interim analysis. However, if the analysis is performed exactly when 416 deaths are observed, the study can be stopped by the DMC for

superiority if the p-value is  $< 0.024$ . An independent statistician from external to BMS will perform the analysis.

If the study continues beyond the interim analysis, the nominal significance level for the final look after 520 deaths would be 0.043. All events in the database at the time of the lock will be used. If number of final events exceeds the number specified per protocol (520 deaths), final boundary will not be recalculated using updated information fraction at interim. In addition to the formally planned interim analysis for OS, the DMC will have access to periodic unblinded interim reports of efficacy and safety to allow a risk/benefit assessment.

Details will be included in the DMC charter.

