**Statistical Considerations:**

**Sample Size:**

The sample size determination of this study is based on OS comparison between subjects randomized to receive nivolumab and sorafenib. With a total of 726 subjects randomized in a 1:1 ratio, approximately 91.5% power will be achieved with an overall type I error 0.05 for OS comparison. The number of events and power for the OS comparison are calculated based on simulation and assuming an exponential distribution for OS in each randomization arm. The study requires at least 520 OS events to ensure approximately 91.5% power to detect a hazard ratio of 0.74 with an overall type I error of 0.05 (two-sided) for OS. The HR of 0.74 corresponds to a 35% increase in the median OS for both non-HCV infected subjects and HCV infected subjects, assuming a median OS of 10 months for non-HCV infected subjects and a median OS of 14 months for HCV infected subjects in the sorafenib arm. One formal interim analysis will be conducted with 80% OS events observed. The stopping boundaries at the interim and final analyses will be derived based on the exact number of deaths using Lan-DeMets alpha spending function with O'Brien-Fleming boundaries. Assuming a piecewise constant accrual rate, it will take approximately 33 months to obtain the required number of deaths for the final OS analysis (13 months for randomization and 20 months for follow-up) and approximately 25 months (13 months for randomization and 12 months for follow-up) for the OS interim analysis.

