#### **Sample size determination for OS**

Based on simulations under the assumptions stated above, approximately 726 subjects will be randomized and followed until at least 520 OS events are observed in order to provide 91.5% power for a hazard ratio of 0.74 with a two-sided type I error of 0.05. This accounts for a group sequential testing procedure with one interim analysis and one final analysis.

The interim analysis will be conducted when 80% OS events are observed. The alpha allocation for the interim and final analyses is based on the Lan-DeMets alpha spending function approach using an O'Brien-Fleming stopping boundary controlling for a two-sided overall type I error of 5%. The stopping boundary will depend on the actual number of deaths at the time of the interim analysis and the final analysis. However, if the interim analysis is performed exactly when 80% OS events are observed, then 0.024 alpha will be used for the interim analysis and 0.043 alpha will be used for the final analysis.

It is projected that an observed hazard ratio of 0.80 or less would result in a statistically significant improvement of nivolumab at the interim analysis of OS; and an observed hazard ratio of 0.84 or

less would result in a statistically significant improvement of nivolumab at the final analysis of OS.

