### **Analysis Timing Projections**

As stated above, approximately 726 subjects will be randomized to the two treatment arms in a 1:1 ratio.

- It will take approximately 13 months to complete the randomization.
- OS interim analysis is projected to occur when there are at least 416 deaths (80% of target events) among approximately 726 randomized subjects, approximately 25 months after the first subject's randomization date (13 months for randomization and 12 months for survival follow-up).
- OS final analysis is projected to occur when there are at least 520 deaths among approximately 726 randomized subjects, approximately 33 months after the first subject's randomization date (13 months for randomization and 20 months for survival follow-up).

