5 SAMPLE SIZE AND POWER

The sample size determination of this study is based on OS comparison between subjects randomized to receive nivolumab and sorafenib. With a total of 726 subjects randomized in a 1:1 ratio to receive nivolumab or sorafenib, approximately 91.5% power will be achieved with an overall type I error 0.05. The sample size determination is based on simulation using R v3.2 for OS. Below are details of the sample size determination.

General assumptions:

- There are assumed 39% HCV-infected subjects among all randomized subjects.
- In the sorafenib arm, median OS is 10 months for non-HCV infected and 14 months for HCV infected.
- Exponential distribution is assumed for OS in each randomized arm.

Estimated cumulated enrollment of randomized subjects is summarized in Table 5-1.

Table 5-1: Estimated Cumulative Number of Randomized Patients

Month	1	2	3	4	5	6	7	8	9	10	11	12	13
HCV	6	17	30	45	61	81	105	131	159	188	218	250	282
Non-HCV	9	25	43	67	98	132	170	210	252	297	345	394	444
All	15	42	73	112	159	213	275	341	411	485	563	644	726

[figure not shown]
Sample size determination for OS

Based on simulations under the assumptions stated above, approximately 726 subjects will be randomized and followed until at least 520 OS events are observed in order to provide 91.5% power for a hazard ratio of 0.74 with a two-sided type I error of 0.05. This accounts for a group sequential testing procedure with one interim analysis and one final analysis. The HR of 0.74 corresponds to a 35% increase in the median OS for both non-HCV infected subjects and HCV infected subjects.

The interim analysis will be conducted when 80% OS events are observed. The alpha allocation for the interim and final analyses is based on the Lan-DeMets alpha spending function approach using an O'Brien-Fleming stopping boundary controlling for a two-sided overall type 1 error of 5%. The stopping boundary will depend on the actual number of OS events observed at the time of the interim analysis and the final analysis. However, if the interim analysis is performed exactly when 80% OS events are observed, then 0.024 alpha will be used for the interim analysis and 0.043 alpha will be used for the final analysis.

It is projected that an observed hazard ratio of 0.80 or less would result in a statistically significant improvement of nivolumab at the interim analysis of OS; and an observed hazard ratio of 0.84 or

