7.5.1 Primary Efficacy Endpoint OS Analyses

7.5.1.1 Primary Analysis

The distribution of OS will be compared in two randomized arms via a two-sided α stratified log-rank test where α will be determined as per [Section 7.5.4.2](#).

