Let $i = 1, 2, 3$ denote index indicating primary endpoint OS and secondary endpoints ORR and PFS, respectively. Accordingly, H_1, H_2, H_3 denote two-sided null hypotheses of no effect in primary endpoint OS and secondary endpoints ORR and PFS, respectively. Let $t = 1, 2$ denote

index indicating interim and final analysis timings, respectively. Correspondingly, $p_{i,t}$ denote nominal p-value of testing H_i at the analysis time t , and the corresponding decision boundaries can be expressed as nominal significance levels $a_{i,t}^*$ such that H_i is rejected if $p_{i,t}$ is smaller than $a_{i,t}^*$ at time t .

To strongly control FWER at level 0.05 across three endpoints and repeated analyses at interim and final analyses, we adopted the stagewise hierarchical testing procedure³⁶ to test H_1 , H_2 , H_3 . Specifically, at the interim analysis time H_1 is tested with nominal significance level $a_{1,1}^*$ leading to the following two possibilities of rejecting H_1 :

[figure not shown]
- If $p_{1,1} < a_{1,1}^*$, H_1 will be rejected, the trial will stop and H_2 will be tested with nominal significance level $a_{2,1}^*$. If $p_{2,1} < a_{2,1}^*$, H_2 will be rejected and H_3 will be tested with nominal significance level $a_{3,1}^*$ with $p_{3,1} < a_{3,1}^*$ leading to the rejection of H_3 . If $p_{2,1} \geq a_{2,1}^*$, H_2 will not be rejected and H_3 will not be tested.
- If $p_{1,1} \geq a_{1,1}^*$, the trial continues to final analysis time and H_1 will be tested with nominal significance level $a_{1,2}^*$. If $p_{1,2} < a_{1,2}^*$, H_1 will be rejected and H_2 will be tested with nominal significance level $a_{2,2}^*$. If $p_{2,2} < a_{2,2}^*$, H_2 will be rejected and H_3 will be tested with nominal significance level $a_{3,2}^*$ with $p_{3,2} < a_{3,2}^*$ leading to the rejection of H_3 . If $p_{2,2} \geq a_{2,2}^*$, H_2 will not be rejected and H_3 will not be tested.

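### Protocol 8.5 appears to freeze the final OS significance level when deaths exceed 520, whereas the synopsis, Protocol 8.1 and the SAP tie it to the actual deaths; the excess error is small

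*Protocol*

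**What the plan says.** Protocol 8.5 plans the interim at 416 deaths and ties the boundary to the actual deaths at the interim only. It gives 0.043 as the nominal level for the final look after 520 deaths. It then says: "All events in the database at the time of the lock will be used". For overrun it adds: "final events exceeds the number specified per protocol (520 deaths), final boundary will not be recalculated using updated information fraction at interim".

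Overrun is built into the design. Under Analysis Timing Projections in Protocol 8.1: "OS final analysis is projected to occur when there are at least 520 deaths among approximately 726 randomized subjects".

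The other places that define the boundary carry no such restriction:

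- Protocol synopsis, Sample Size: "The stopping boundaries at the interim and final analyses will be derived based on the exact number of deaths using Lan-DeMets alpha spending function".
- Protocol 8.1: "The stopping boundary will depend on the actual number of deaths at the time of the interim analysis and the final analysis".
- SAP 5, with the same sentence in SAP 7.5.4.2: "The stopping boundary will depend on the actual number of OS events observed at the time of the interim analysis and the final analysis".

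SAP 7.5.1.1 takes the alpha for the primary OS test from SAP 7.5.4.2. The purpose given there is: "To strongly control FWER at level 0.05 across three endpoints and repeated analyses at interim and final analyses".

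**The concern.** Once deaths exceed 520, a reader can cite current text for two different final levels: the value fixed at 520 deaths, or a value re-solved for the actual count. The SAP's error-spending method points to the second, but it neither repeats nor overrides the sentence in Protocol 8.5.

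The two are not equivalent. The correlation between the interim and final log-rank statistics is the square root of interim deaths over final deaths. As final deaths rise above 520 this correlation falls, the two looks become less redundant, and an unchanged final critical value spends more than the alpha left after the interim. This level decides the only primary endpoint and opens the hierarchical tests of ORR and PFS, so it should have one value fixed in advance.

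**Working it through.** **Inputs.** Overall two-sided alpha 0.05, interim at 80% of events, levels 0.024 and 0.043, HR 0.74 and 91.5% power (Protocol 8.1, SAP 5); 416 and 520 deaths (Protocol 8.1, 8.5); monthly accrual by HCV status (SAP Table 5-1); sorafenib medians 14 months (HCV) and 10 months (non-HCV) (Protocol 8.1, SAP 5). Below, I is interim deaths, D is final deaths, c1 and c2 are the critical values at the two looks.

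**Step 1: reproduce the plan's levels.** Lan-DeMets O'Brien-Fleming-type spending with 0.025 per side is 2[1 − Φ(z(0.9875)/√t)]. At t = 416/520 = 0.8, doubled for two sides, it gives 0.02442 (c1 = 2.2504). Solving 1 − P(|Z1| < c1, |Z2| < c2) = 0.05 with correlation √0.8 gives c2 = 2.0250, a nominal level of 0.04287. These match the stated 0.024 and 0.043. The critical HRs exp(−2c/√deaths) are 0.802 and 0.837, against the stated 0.80 and 0.84.

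**Step 2: overrun.** Keep c1, set the correlation to √(416/D), and either hold c2 at 2.0250 (frozen) or re-solve c2 for 0.05 (remaining alpha).

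| Final deaths D | Overall error, frozen | Final level from remaining alpha |
|---|---|---|
| 520 | 0.0500 | 0.0429 |
| 526 | 0.0503 | 0.0425 |
| 540 | 0.0509 | 0.0418 |
| 580 | 0.0524 | 0.0400 |
| 600 | 0.0531 | 0.0392 |

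The critical HR, frozen versus remaining alpha, is 0.8401 versus 0.8393 at 540 deaths and 0.8452 versus 0.8432 at 580. The OS decision differs only for a p-value between 0.0418 and 0.0429 at 540, or between 0.0400 and 0.0429 at 580.

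**Step 3: sensitivity to rounding.** With both levels rounded (0.024 and 0.043), the error is 0.0499 at 520, 0.0502 at 526, 0.0508 at 540 and 0.0523 at 580. With the exact interim boundary and exactly 0.043 at the end, it is 0.0504 at 526 and 0.0525 at 580.

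**Step 4: sensitivity to interim timing.** Here the final level is set from I/520 and then frozen.

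| Interim deaths I | Spent at interim | Final level set at 520 | Error at D = 540 | Error at D = 580 |
|---|---|---|---|---|
| 406 | 0.0224 | 0.0434 | 0.0508 | 0.0522 |
| 416 | 0.0244 | 0.0429 | 0.0509 | 0.0524 |
| 436 | 0.0287 | 0.0418 | 0.0512 | 0.0531 |

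If exactly 0.043 were used whatever the interim count, the error at 526 deaths would be 0.0496 with the interim at 400 and 0.0508 with it at 425.

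**Step 5: how much overrun to expect.** Table 5-1 accrual (uniform within each month), exponential survival, the stated medians, HR 0.74 and no dropout (an assumption) give 525.9 deaths at month 33, the projected time of the final analysis. The 520th death is expected at month 32.4.

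**The case against.** The strongest reply is that the sentence in Protocol 8.5 bars only one operation: recomputing the final boundary with the interim information fraction restated as 416/D. Barring that is right. Restating the fraction would raise the final level to 0.0437 at 540 deaths and 0.0451 at 580. Because the interim boundary has already been used, the true error would then be 0.0516 and 0.0543, worse than freezing. On this reading Protocol 8.5 does not conflict with the other sections, and SAP 7.5.4.2, which supplies the OS alpha, already gives the answer.

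This reading is possible and may be what was meant. It does not close the gap. Nothing in Protocol 8.5 says that the final value is otherwise re-solved. The surrounding sentences tie only the interim boundary to actual deaths and name 0.043 for the final look. A reader who applies 0.043 at 540 deaths is following the text.

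Other points on that side stand. The excess at 526 deaths, 0.0003, is about the size of the rounding effects in Step 3. The counts above 526 have no source in the documents. Nothing shows that a frozen level was actually used. SAP 7.10 records the final OS database lock on June 05, 2019, so new wording cannot change how the test was prespecified. These points limit the severity; they do not make the sections agree.

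**Conclusion.** The concern holds and is minor. Under overrun, current text supports two final OS levels, and the frozen one exceeds the 0.05 that SAP 7.5.4.2 says is strongly controlled. With the interim at exactly 416 deaths and the unrounded final level 0.0429, the excess is 0.0003 at 526 deaths, 0.0009 at 540 and 0.0024 at 580, and zero at 520.

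The sizes depend on the interim and final death counts, which the documents do not give. The 526 figure further assumes no dropout and a final cutoff at month 33. The practical consequence is confined to an OS p-value falling in the narrow band between the two levels.

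**What to change.** Align Protocol 8.5 and SAP 7.5.4.2 with one sentence in each, for example: *The alpha spent at the interim is fixed at the value used there; the final critical value is solved from the remaining alpha with correlation equal to the square root of interim deaths over final deaths, including when final deaths exceed 520.* This keeps the sound part of Protocol 8.5, that the interim spend is not restated, and removes the ambiguity about the final value.

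Because the database is locked, the useful step now is disclosure. Report with the OS result the interim and final death counts, the level applied and how it was derived. If deaths exceeded 520, show the OS p-value against both the frozen and the remaining-alpha level, and do not present that comparison as prospective.

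The cost is one sentence per document and one software run; after the lock it is a reporting statement only. The threshold becomes slightly stricter under overrun. With the interim at 416 and HR 0.74, power falls from 93.4% to 93.3% at 540 deaths and from 94.9% to 94.6% at 580, still above the planned 91.5%.
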